This is a R34 pilot study funded by NIMH as part of the Johns Hopkins NIMH P50 Center to Accelerate Translation of Interventions to Decrease Premature Mortality in Serious Mental Illness. In this study, we will pilot test an adapted Comprehensive Unit Safety Program (CUSP) implementation strategy to improve mental health providers' delivery of evidence-based CVD risk factor care for individuals with SMI in Maryland health homes. CUSP is a quality improvement strategy developed by the JHU Armstrong Institute for Patient Safety and Quality³⁶ and used to improve care delivery in other, primarily inpatient, contexts.³⁷⁻⁴⁵ CUSP is more recently being applied to outpatient quality improvement.⁴²⁻⁴⁵ Our study is the first to adapt CUSP for the community mental health setting.

This study will result in an adapted set of CUSP tools and resources for community mental health programs, which other community mental health programs can use in the future. Study results will lay the foundation for development and evaluation of a scalable model for implementation of evidence-based physical health care in community mental health settings.

2. Objectives (include all primary and secondary objectives)

The project will pilot test a comprehensive unit-based safety program (CUSP) to implement evidenced-based practices to guide delivery of care for hypertension, dyslipidemia and diabetes for persons with serious mental illness in Maryland Medicaid health homes. The project will characterize implementation processes, organizational and provider-level factors, and cardiovascular disease risk factor care and control.

The specific aims are:

Aim 1. Characterize implementation barriers, quality improvement culture, providers' self-efficacy, and CVD risk factor care and control in Maryland Medicaid SMI health home programs. Using observation, focus groups, surveys, and database abstraction, we will answer 4 research questions:

1. What are the barriers to delivery of evidence-based CVD risk factor care at health home sites, and what strategies could help to overcome those barriers?
2. How supportive of quality improvement is the current health home culture?
3. How do providers rate their self-efficacy to deliver/coordinate evidence-based CVD risk factor care?
4. At the health home study sites, what are baseline rates of evidence-based care for and control of hypertension, dyslipidemia, and diabetes mellitus?

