Aim 2. Pilot test a comprehensive unit-based safety program (CUSP), designed to implement an evidence-based practice bundle, in Maryland Medicaid SMI health home programs. We hypothesize CUSP will:

1. Improve the organizational culture surrounding delivery of evidence-based CVD risk factor care.
2. Improve providers' self-efficacy to deliver evidence-based CVD risk factor care.
3. Yield preliminary data showing increased rates of evidence-based care for and control of hypertension, dyslipidemia, and diabetes among consumers with SMI.
4. Be perceived as acceptable, appropriate, and feasible by health home providers.

3. Background (briefly describe pre-clinical and clinical data, current experience with procedures, drug or device, and any other relevant information to justify the research)

Persons with serious mental illness (SMI) experience high prevalence and poor control of cardiovascular disease (CVD) risk factors including hypertension, dyslipidemia, and diabetes mellitus;¹⁻⁹ poor control is driven in part by low rates of guideline-concordant CVD risk factor care in this group.^{10,16-18} Our team's data from a trial⁴⁶ of 269 adults with SMI in Maryland

shows that 84% have hypertension, diabetes mellitus, or dyslipidemia and 45% meet clinical definitions of poor control for at least one of these conditions.

The historic separation of the general medical and mental health systems contributes to deficits in care quality by impeding access, communication, and sharing of data and expertise across systems.^{27,47-52} In recent years, programs designed to integrate primary care services, like CVD risk factor management, into specialty mental health settings – where many people with SMI receive the majority of their care^{24,26,27} – have been implemented at the federal, state, and local levels.^{33,53,54} Maryland’s Medicaid health home program, implemented in October 2013, is one such model.⁵⁵

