CUSP is a scalable quality improvement strategy developed by the JHU Armstrong Institute for Patient Safety and Quality used to improve collaboration and improve patient safety and quality of care. A foundation of CUSP is the CUSP “team” that implements the patient safety and quality processes, in order to increase delivery of care as defined in the evidence-bundle. Each health home program will form a CUSP team that will participate in advanced CUSP training and implement the CUSP process over the course of the project. The CUSP team will have approximately five to ten members including health home program staff and an organizational leader. The CUSP process and trainings will follow standard formats used and evaluated in prior CUSPs.^{37-45,64}

Timeline for CUSP

Before CUSP: 1 month. The CUSP team will participate in trainings outlined below (Table 1) as part of the pre-implementation period.

CUSP Implementation: 12-months, monthly meetings. During the implementation period the CUSP team will meet monthly for one hour for a meeting guided by study team expert CUSP facilitators focused on problem-solving through a team-based quality improvement process. At these meetings the CUSP team will review issues, problems or events regarding the

cardiovascular care of health home clients/patients. Health homes already measure CVD risk factor care but without using standard processes. As part of implementing the evidence-bundle on management of CVD risk factors, care coordination and population health, CUSP team members will use a standard population health spreadsheet template that the study team provides to track CVD risk factors and care processes during regular health home program care. Using the spreadsheet, CUSP team members can aggregate patient-level data and identify trends in CVD risk factor prevalence and quality of care metrics for persons enrolled in the health home. Team members will identify problems in the care delivery process and use worksheets and guides to brainstorm processes and procedures as a team to improve care. They will then implement and develop how the process or procedure will be evaluated.

CUSP Sustainment: 3-months. CUSP implementation will be followed by a 3-month sustainment period in which the CUSP team will continue to use evidence-based care practices and follow the CUSP process without our team's expert facilitators.

CUSP Training Overview

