Sustaining a CUSP Team	CUSP team and all psychiatric rehabilitation program staff	60 minutes	

Data Collection:

Study data collection is outlined in Table 2 and in more detail below. Study team involvement in data collection is all virtual/remote.

Table 2. Study Data Collection			
Qualitative Data Collection	Who	Estimated time	When
CUSP Team Focus Groups	Selected CUSP team members (~5 per site)	60 minutes	Baseline, 15 months
Primary Care Provider Interviews	Primary care providers caring for health home program patients but who are not health home team members (~5 per site)	30 minutes	Baseline
Survey Measures			
Demographic Characteristics: age, sex, race, ethnicity, length of time at program, role in program, previous Motivational Interviewing training, comfort with technology	Health home team and psychiatric rehabilitation program staff (~30 per site)	~5 minutes	Baseline
Implementation Climate: This is a measure of the degree to which an organization supports evidence-based practice implementation	Health home team and psychiatric rehabilitation program staff (~30 per site)	~3 minutes	Baseline
Quality Improvement Culture: Measured using a modified version of the validated 42-item Survey on Patient safety used in inpatient CUSPs	Health home team and psychiatric rehabilitation program staff (~30 per site)	~5 minutes	Baseline, 12 months

Pre-Implementation Health Homes Survey: The nurse care manager will assess the behavioral health home's database and what is currently tracked.	CUSP team member (health home nurse/nurse care manager) (1 per site)	~10 minutes	Baseline
Self-Efficacy: Self-efficacy to deliver evidence-based CVD risk factor	CUSP team (~10 per site)	~5 minutes	Baseline, 12 months
Acceptability, Appropriateness, and Feasibility of the Intervention Implementation Strategies: Measured with a brief 4-item practice instrument (AIM, IAM, FIM) ⁶⁷	CUSP team (~10 per site)	~5 minutes	Baseline, 12 months
Acceptability, Appropriateness, and Feasibility of the Evidence-Based Practice Bundle: Measured with a brief 4-item practice instrument (AIM, IAM, FIM) ⁶⁷	CUSP team (~10 per site)	~5 minutes	Baseline, 12 months
Motivation: Degree to which providers and staff agree or disagree with statements that deal with aspects of the health homes intervention to improve cardiovascular risk factor care	CUSP team (~10 per site)	~3 minutes	Baseline, 12 months

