Beliefs about Motivational Interviewing Questionnaire	CUSP team (~10 per site)	~2 minutes	Baseline, 3, 6, 12 months
Importance and Confidence of Using Motivational Interviewing	CUSP team (~10 per site)	~2 minutes	Baseline, 3, 6, 12 months
Perceived Usefulness	CUSP team (~10 per site)	~2 minutes	12 months
Fidelity Measures			
Avatar Motivational Interviewing Performance Measurements: from use of motivational interviewing techniques in simulated online conversations	CUSP team (~10 per site)	15 minutes	Baseline to 3 months (weekly requested), 6, 12 months
Fidelity to Motivational Interviewing: Standardized Actor Interviews will be conducted to assess fidelity to motivational interviewing.	CUSP team (~10 per site)	30 minutes	Baseline, 3, 6, 12 months
Health Home Enrollee Measures			
Sociodemographic and Mental Health: age, gender, race, ethnicity, living arrangement, disability status, any issues with transportation, scheduling or obtaining medications, primary diagnosis, categories of psychotropic medications used	All health home enrollees (patients) (~200 per site) Collected by CUSP team/ health home staff during regular health home program care		Baseline, 6, 12 months
CVD risk factors: weight, BMI, tobacco smoking status, blood pressure, diabetes, HgbA1c, lipids, diagnoses of hypertension, diabetes, dyslipidemia, CVD risk scores			
Evidence-Based CVD Risk Factor Care: % of consumers eligible to receive each care process in the evidence bundle who receive that process (e.g., statin prescription, diabetes foot exam, follow-up visits)			
CVD Risk Factor Control: % of consumers meeting clinical criteria for having controlled hypertension (eg BP< 130/80) dyslipidemia, and diabetes (HgbA1c<7.0)			

Qualitative Data Collection

CUSP Team Focus Groups: ~ 5 selected CUSP team members per site will be asked to participate in focus group interviews by Zoom. These focus groups will be 60-minutes and conducted by our research team using a semi-structured guide. Focus groups will be audio or video-recorded, and recordings will be transcribed using Production Transcripts, Inc.

Primary Care Provider Interviews: ~5 primary care providers per site who provide care for health home enrollees and coordinate care with but are not formally part of the health home team will participate in a ~30-minute interview by phone or Zoom. Interviews will be audio or video-recorded, and recordings will be transcribed using Production Transcripts, Inc.

Surveys

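### Enrollee outcomes come from a spreadsheet that is itself a CUSP tool, so Section 7 cannot tell a change in recording from a change in care or control

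*Combined protocol and SAP*

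**What the plan says.** All places are in the combined protocol and SAP.

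- **Recording before CUSP.** Section 4, under CUSP Implementation: "Health homes already measure CVD risk factor care but without using standard processes". Section 3 adds that systems for tracking guideline care are lacking, with HbA1c monitoring as its example.
- **The tool.** The study team supplies a standard spreadsheet as part of putting the evidence bundle into practice. Teams are to use it to "identify trends in CVD risk factor prevalence and quality of care metrics".
- **The outcome source.** Under Health Home Enrollee Measures, the same data serve the evaluation. Table 2 says they are "Collected by CUSP team/ health home staff during regular health home program care". Diagnoses, values and care processes are all among these measures. Under Data Management, sites deposit the file at baseline, 6 and 12 months, with dates for process measures.
- **No comparison.** "Each health home program will form a CUSP team", and Section 4 item e marks a non-treatment group as not applicable.
- **The analysis.** Section 7 fits a multi-level model to the three waves and presents it as evaluating what CUSP does to enrollee care and control. It gives no rule for blanks, outdated values or new diagnoses.
- **Related provisions.** A baseline survey asks the nurse care manager about the site's "database and what is currently tracked". Aim 1 mentions database abstraction. Section 7 uses neither for this purpose.

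**The concern.** The outcomes are percentages of eligible enrollees who received a process or met a control criterion. The records decide who is eligible, who has a value and who counts as a success. If CUSP makes those records fuller, numerator and denominator can both move without any change in treatment or in blood pressure, HbA1c or lipids. Better tracking is an intended result of CUSP, but it is not the same result as better control.

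Aim 2 asks only that the study "Yield preliminary data showing increased rates of evidence-based care for and control of hypertension, dyslipidemia, and diabetes among consumers with SMI". Even so, the results are meant to "lay the foundation for development and evaluation of a scalable model", and Section 7 also tests mediators and moderators on these outcomes. A recording change taken for a care change would carry into both. A real gain could equally be masked.

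**Working it through.** The plan gives no completeness rates, effect size or power calculation, so there is no figure to reproduce. What follows shows the mechanism, not an estimate of its size. Every scenario assumes **no true change**.

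**Inputs.** From Section 3 (a prior trial of 269 adults): "84% have hypertension, diabetes mellitus, or dyslipidemia and 45% meet clinical definitions of poor control for at least one of these conditions". All completeness rates, care rates and case counts below are assumed.

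**1. A plausible level of control.** Among people with at least one condition, 1 − 0.45/0.84 = 0.464. This is an any-condition composite and not a planned outcome.

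**2. Blanks counted as not controlled.** Observed rate = p × completeness.
- 0.464 × 0.70 = 0.325 and 0.464 × 0.90 = 0.418, a difference of +9.3 points.
- In general the false change is p × the gain in completeness. It runs from 0.30 × 0.10 = +3 points to 0.70 × 0.30 = +21 points.

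**3. Blanks excluded.** With a and b the shares of controlled and uncontrolled people who have a value, observed rate = p·a / (p·a + (1 − p)·b). With 90% of both groups recorded at 12 months:

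| Baseline a / b | Blanks excluded | Blanks not controlled |
|---|---|---|
| 70% / 70% | 46.4 → 46.4 (0) | 32.5 → 41.8 (+9.3) |
| 80% / 60% | 53.6 → 46.4 (−7.2) | 37.1 → 41.8 (+4.6) |
| 60% / 80% | 39.4 → 46.4 (+7.0) | 27.9 → 41.8 (+13.9) |

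Differences are taken before rounding. In the second row, the sign depends on a rule that the plan does not state.

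**4. New diagnoses.** Take 300 recorded cases at 60% throughout, and add 60 newly recorded ones.
- New cases at 30%: (180 + 18)/360 = 55.0%, a change of −5.0.
- New cases at 80%: (180 + 48)/360 = 63.3%, a change of +3.3.

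These are pooled proportions, not output from the planned model.

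**5. Care processes.** With true receipt of 60%, let the share of services never documented fall from 20% to 10%. Then 0.60 × 0.80 = 0.48 becomes 0.60 × 0.90 = 0.54, a change of +6.

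**6. Does the proposed rule behave?**
- Row 1 gives +9.3 or 0 according to the blanks rule, and row 2 changes sign, so neither supports a claim.
- In the new-diagnosis example, the fixed cohort of 300 stays at 60%, so its change is 0.
- Row 3 rises under both rules. The fix would not catch it.
- Direction alone is too weak a test. In a simulation with no true change (840 people, completeness 70% then 90%), the all-enrollee and within-person results moved the same way in about 46–48% of runs. The within-person 95% interval lay above 0 in only about 2%.
- If baseline recording depends on control, even the within-person estimate drifts by about 3 to 5 points, in either direction.

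**The case against.** The strongest case on the other side has five parts.

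- **Non-standard is not the same as incomplete, and the template is also deposited at baseline.** This stands in part. A reader might infer that baseline and follow-up use different forms; the documents do not support that. Aim 1's database abstraction could also fill the baseline cells well. But the plan does not say how those cells are filled from existing records, or whether this happens before or after the training month. Section 3 itself calls tracking systems lacking.
- **For monitoring, recording and care overlap.** This stands. A newly dated HbA1c may be care newly given, and a new diagnosis may be true case finding. The fix has to allow for it.
- **The +9.3 needs one particular blanks rule.** This stands. The figure is an illustration only.
- **A multi-level model may resist changes in who is counted.** This stands in part. Suppose the 300 cases truly improve from 60% to 65% and 60 new cases enter at 30%. The pooled rate is then (195 + 18)/360 = 59.2%, a change of −0.8. A simulated linear mixed model with a person-level intercept (assumed probit person SD 1 to 2) gave about +1.0 to +2.7 instead. The gain is attenuated, not reversed. Section 7 does not name its levels, and no model repairs an unrecorded service scored as not received.
- **This is an uncontrolled five-site pilot.** This stands, and it argues for a modest remedy. It does not justify the causal wording.

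**Conclusion.** The concern holds as a matter of design. Non-standard recording beforehand, a CUSP tool as the outcome source, CUSP at every site and a three-wave change read as CUSP's effect are all in the text. As written, Section 7 could credit CUSP with a recording change or miss a real gain. It should be fixed before analysis.

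The size is unknown. A reader might infer that recording will improve, that the bias is upward, or that about 9 points of any gain would be artefact. The documents support none of these: they give no completeness rates and no blanks rule, and the direction depends on both. Confidence attaches to the mechanism, not to any figure above.

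**What to change.** Amend Section 7 as follows.

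1. **Completeness.** By measure, site and wave, report the percentage of eligible enrollees with a recorded value and the number with each diagnosis. State one rule for blanks (counted as not met, or excluded), with a sensitivity analysis under the other.
2. **Fixed cohort.** Keep the planned multi-level model on all enrollees. Alongside it, fit the same model, on all three waves, to enrollees whose diagnosis was recorded at baseline. Show newly recorded diagnoses, joiners and leavers separately.
3. **Care processes.** Where service dates exist, score by service date, with the same look-back window and documentation lag at every wave. Otherwise label the outcome as documented care. Where the test is itself the care process, count a newly dated test as care received.
4. **Wording and claims.** For these outcomes, say change over time rather than effects of CUSP. Describe better care or control only if the 95% interval from (2) or (3) excludes no change and the conclusion holds under both blanks rules. Excluding blanks tells nothing for an item entered only when done, because the rate is then 100% at every wave; say so where this applies. Do not rely on two analyses merely moving the same way, and do not report the gap between models as the amount of recording change.

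**Cost.** Section 7 text, tables and some added programming. Study IDs and process dates are already planned, so no new data are needed. The fixed cohort is smaller and covers only people diagnosed at baseline. State as limits recording that depends on the value (row 3 of the table), regression to the mean, secular trends and services never documented (the +6 example).

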Study team members will conduct trainings (Table 1) by Zoom while the study is remote.

All psychiatric rehabilitation program and health home leaders/providers/staff participate in a brief CUSP Process Training that introduces the principles of CUSP, and at the end of the 12-month implementation phase, in a training about sustaining CUSP.⁶⁴

The CUSP team participates in advanced CUSP training including training in the evidence-bundle. The evidence-bundle focuses on evidence-based CVD risk factor guidelines and care coordination/ population health management for CVD risk factors in persons with SMI. The evidence-bundle training also includes content in motivational interviewing as a key-component of helping clients with SMI make healthy behavioral change.

The real-time motivational interviewing training will be supplemented with an online avatar practice module.^{65,66} The avatar practice module includes a 15-minute didactic component where providers learn about motivational interviewing and techniques that can be used to guide patients with SMI toward health changes, and 15-minute practice conversations where providers take on the role of virtual provider avatar and practice the use of motivational interviewing techniques in simulated conversations about managing cholesterol in persons with serious mental illness using patient avatars on the Kognito platform. We will recommend CUSP team members practice weekly for the first three months. An online dashboard will give CUSP team members an individualized report on their performance each time they practice.

Table 1. CUSP Training			
Topic	Who receives training	Estimated Length	
CUSP Process Training - Introductory Introduces the Principles of CUSP	CUSP team and all psychiatric rehabilitation program staff	60 minutes	
CUSP Process Training- Advanced 1. Introduction to CUSP and Science of Quality 2. Creating Engagement and Ownership of CUSP 3. Identifying and Learning from Challenges 4. Kicking off CUSP	CUSP team	Four one-hour sessions	
Evidence Bundle (evidenced-based practices) for CVD risk factors and care coordination/population health management	CUSP team	Two two-hour sessions	
Evidence Bundle Motivational Interviewing for CVD risk factor management	CUSP team	Two two-hour sessions	
Motivational Interviewing for CVD risk factor management – using Avatar	CUSP team	Recommended weekly 15-minute practice sessions for three months and then as needed/desired	

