Motivation: The CUSP team (~10 per site) will take this survey. Measured by assessing the degree to which providers and staff agree or disagree with statements that deal with aspects of the health homes intervention to improve cardiovascular risk factor care. Categories include expectancy, instrumentality, and valence regarding the evidence-based CVD risk factor care bundle and the CUSP quality of care process.

Beliefs about Motivational Interviewing Questionnaire: The CUSP team (~10 per site) will take this survey. A 7-question survey assessing the extent to which each person agrees with statements about motivational interviewing.

Importance and Confidence of Using Motivational Interviewing: The CUSP team (~10 per site) will take this survey. A 6-question survey assessing the importance and confidence each person has with motivational interviewing.

Perceived Usefulness: The CUSP team (~10 per site) will take this survey. A 6-question survey assessing the perceived usefulness of the motivational interviewing avatar platform during the course of the project.

Fidelity Measures

Avatar Motivational Interviewing Performance Measurements: Members of the CUSP team (~10 per site) will use the avatar platform and have 15-minute practice “conversations” where they practice use of motivational interviewing techniques in simulated conversations about managing cholesterol with patient avatars. An online dashboard will give CUSP team members an individualized report on their performance each time they practice.

Fidelity to Motivational Interviewing: Standardized Actor Interviews: Members of the CUSP team (~10 per site) will participate in 30-minute audio-recorded phone interviews with standardized patient actors. These standardized patient actors are trained actors playing roles of patients with SMI and CVD risk factors.

Health Home Enrollee Measures

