As part of implementing the evidence-bundle on management of CVD risk factors, care coordination and population health, CUSP team members will be using a standard population health spreadsheet template that the study team provides to track CVD risk factors and care processes during regular health home program care. Using the spreadsheet, CUSP team members can aggregate patient-level data and identify trends in CVD risk factor prevalence and quality of care metrics for persons enrolled in the health home. This data (in a limited dataset) will also be used for study evaluation purposes. Health home enrollee data will include sociodemographic and basic mental health diagnosis/medication categories, CVD risk factors, evidence-based CVD risk factor care processes and CVD risk factor control.

Data Management:

Qualitative data. Interview and focus group data will be audio or video-recorded and

recordings will be transcribed using Production Transcripts, Inc or another approved Johns Hopkins vendor. Names will be removed from transcripts. Recordings will be stored in a Johns Hopkins secure network drive and will be destroyed when analyses are complete. Standardized actor interview recordings will be reviewed by experts in motivational interviewing for fidelity to motivational interviewing practices and stored in a Johns Hopkins secure network drive or OneDrive.

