Quantitative data. Each participant will be assigned a unique study ID number for data collection. We will store data in a Johns Hopkins REDCap database. Study team members are trained to protect integrity and confidentiality of the data. Kognito, a health simulation company, developed the avatar simulations for this project and hosts the avatar training platform and dashboard. Avatar performance measurement data for motivational interviewing practice conversations is accessible only by the individual study participant (CUSP team member) and the study team, not shared outside Kognito. Kognito stores data securely behind two firewalls. For health home enrollee measures, the CUSP team will use participant initials and a study ID number in the Excel population health tracking spreadsheet. Participant names, used for implementing the evidence-bundle, will be removed by the CUSP team. They will use Johns Hopkins OneDrive, available to non-Johns Hopkins collaborators, to deposit the spreadsheet at baseline, 6 and 12 months. The data will contain no names or birthdates but will have dates of process measures (e.g., lab values) thus it will be a limited dataset. Each study site will only be able to access a folder specific to their site, and spreadsheets will have password protection.

- c. Blinding, including justification for blinding or not blinding the trial, if applicable.
N/A
- d. Justification of why participants will not receive routine care or will have current therapy stopped. N/A
- e. Justification for inclusion of a placebo or non-treatment group N/A
- f. Definition of treatment failure or participant removal criteria. N/A
- g. Description of what happens to participants receiving therapy when study ends or if a participant's participation in the study ends prematurely. N/A

5. Inclusion/Exclusion Criteria

Psychiatric rehabilitation program and health home team staff, including providers and leadership are those employed by the psychiatric rehabilitation program or health home program. All are adults and English-speaking.

Primary care providers are those who provide primary care to health home enrollees.

Health home enrollees are by definition persons with serious mental illness who are members of a behavioral health home. All are 18 years and older.

6. Drugs/ Substances/ Devices-N/A

- a. The rationale for choosing the drug and dose or for choosing the device to be used.

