For qualitative data, no focus group participants will be individually identified; a site identifier will be used. The link to the site ID will be held in a locked file. Focus group transcripts will have names (if mentioned during the group) removed, and no participants will be identified by name in any publications. Furthermore, data will not be presented in such a way that their identity can be inferred. Similar procedures will be used for interviews. Psychiatric rehabilitation program/health home directors will give assurance to providers/staff that their participation and information shared will not affect their employment or their evaluation. Data will not be presented in such a way that identity can be inferred. As described in Data Management, data will be stored in Johns Hopkins secure drives.

For quantitative data, as in Data Management above, each staff participant will be assigned a unique study ID number for data collection and data will be stored in REDCap. For health home enrollee measures from the population health spreadsheet, we will request a waiver of informed consent. The study team will receive limited datasets from health home program sites in Johns Hopkins OneDrive with study IDs. The data will have dates of process measures (e.g., lab values) but no names or birthdates. Folders and spreadsheets will have password protection.

9. Benefits

a. Description of the probable benefits for the participant and for society.

There is no benefit to individual participants. This research will help stakeholders have a greater understanding of the organizational and staff-level barriers to delivery of evidence-based cardiovascular risk factor care in community mental health settings.

10. Payment and Remuneration

- a. Detail compensation for participants including possible total compensation, proposed bonus, and any proposed reductions or penalties for not completing the protocol.

Primary care providers will be paid \$50 for completing an interview. CUSP team members will be paid \$50 for participating in a focus group and will be paid \$25 for each standardized actor interview. CUSP team members will be compensated \$25 for completion of surveys administered at baseline and 12-month data collection and \$10 for completion of surveys at all other time points. Psychiatric rehabilitation program staff, who are not part of the CUSP team will receive \$10 for completion of surveys at baseline and 12 months.

11. Costs – N/A

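### Does the protocol's silence on rater masking and rating order for the standardized actor recordings call for a change to the plan?

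*Combined protocol and SAP*

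**What the plan says.** Table 2 (Fidelity Measures) lists the measure with the purpose that "Standardized Actor Interviews will be conducted to assess fidelity to motivational interviewing", in about 10 CUSP team members per site at baseline, 3, 6 and 12 months. The Fidelity Measures text in Section 4 adds that members "will participate in 30-minute audio-recorded phone interviews with standardized patient actors".

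The only sentence on assessment is under Data Management, in the paragraph on qualitative data: "Standardized actor interview recordings will be reviewed by experts in motivational interviewing for fidelity to motivational interviewing practices". It names no instrument, number of raters, agreement check, masking or rating order.

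Two entries in Section 4 come near the subject without settling it. Item 4c, on blinding the trial, is marked not applicable. Item 4e reads "Justification for inclusion of a placebo or non-treatment group N/A", which fits a study in which all five sites receive CUSP.

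**The concern.** Fidelity to motivational interviewing is an expert's judgement of a conversation, and the staff being judged have been trained in it: "The evidence-bundle training also includes content in motivational interviewing as a key-component of helping clients with SMI make healthy behavioral change". An expert who knows that a recording is from 12 months has a reason to hear improvement. An expert who rates recordings as they arrive may become stricter or more lenient over the year, and that shift would line up with visit. With no comparison group, neither effect could be separated from real change.

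The measure also has a purpose. Section 2 states that "The project will characterize implementation processes, organizational and provider-level factors, and cardiovascular disease risk factor care and control", and four repeated assessments invite a report of change. What would be at stake is the credibility of such a report, in a pilot meant to lay the foundation for a scalable model.

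**Working it through.** **1. Where the measure is used.** I compared it with each commitment in the plan.

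- Aim 2 hypotheses (Section 2): organizational culture; provider self-efficacy; rates of evidence-based care and risk factor control; acceptability, appropriateness and feasibility. Actor-interview fidelity is not among them.
- Section 7, main analyses: pre/post culture and self-efficacy; enrollee care and control at baseline, 6 and 12 months; mediation by culture and self-efficacy, with moderation by implementation climate. Actor-interview fidelity is not an outcome, mediator or moderator.
- Section 7, remainder: descriptive statistics for acceptability, feasibility and appropriateness, and thematic coding of interview and focus group transcripts. In Section 4, transcription is described for the focus groups and the primary care provider interviews. The actor interviews are described only as recorded and reviewed. Even if they were coded for themes, that would not produce a fidelity change score.

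Bias in the actor ratings therefore has no route into a planned result.

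**2. Volume.** Inputs: 5 sites; about 10 members per site (Table 2), or 5 at the low end, since "The CUSP team will have approximately five to ten members including health home program staff and an organizational leader"; 4 time points; 30 minutes each. All interviews are assumed completed.

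- Upper: 5 × 10 × 4 = 200 recordings; 200 × 0.5 h = 100 h.
- Lower: 5 × 5 × 4 = 100 recordings; 100 × 0.5 h = 50 h.

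**3. What rating order could do.** The plan has no figure to reproduce. Four assumptions are mine: a numeric score, a single rating sequence, drift of total size D that is linear from the first rating to the last, and n recordings per visit, so that N = 4n.

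In visit order, the drift in the change from baseline at follow-up k (1, 2, 3 for 3, 6, 12 months) is k·n/(N − 1) × D.

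- n = 50, N = 200: 50/199 = 0.251; 100/199 = 0.503; 150/199 = 0.754.
- n = 25, N = 100: 25/99 = 0.253; 50/99 = 0.505; 75/99 = 0.758.

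In fully mixed random order the mean is 0 and the SD is √(2·S²/n) × D, with S² = N(N + 1)/[12(N − 1)²].

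- n = 50: S² = 200 × 201/(12 × 199²) = 0.0846; SD = √(2 × 0.0846/50) = 0.058.
- n = 25: S² = 100 × 101/(12 × 99²) = 0.0859; SD = √(2 × 0.0859/25) = 0.083.

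These are fractions of D. The documents give no D, and it may be zero. Several raters, batching by site or non-linear drift would change the fractions.

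**4. Expectation.** If a rater who knows the visit adds b to every post-baseline score, the change is biased by b in any rating order. Only masking addresses that, and only in part, because what is said on a recording may reveal the visit. The documents give no b.

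**5. What remains open.** The recordings are kept on secure storage, so files can be coded and mixed when rating is organized, without any protocol text. Mixing all time points means rating cannot start until the 12-month recordings exist. Baseline recordings then wait about 12 months, and the 50 to 100 hours fall together. No section uses the actor results earlier; the individual feedback described comes from the avatar dashboard.

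**The case for a change.** The strongest case for a change is that the measure costs staff time, participant payments and expert review, so it should yield something interpretable. A random list and coded file names are cheap, and random order protects against drift even where masking fails. The not-applicable entry on blinding answers a question about treatment allocation, not about raters. Removing names from transcripts and assigning study IDs do not hide the visit.

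All of that is right as description. The silence is genuine, and coded files in mixed order would be good practice if change in fidelity is reported. What does not follow is that the plan is unsound without the text. Harm needs an unplanned report of change, together with raters who know the visit or who drift, and the documents show none of these.

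The cost is also less certain than it looks. The payment "for each standardized actor interview" goes to CUSP team members for taking part and says nothing about rater time or funding. Masking to site would not help, because the worry is change over time and no between-site fidelity comparison is stated. Masking and order also come second to the more basic open points: what is scored, by how many raters and with what agreement.

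The actor review is not the only evidence on this skill. Avatar performance is a second fidelity measure, collected from baseline to 3 months and at 6 and 12 months, reported by the platform with no expert review described. It has its own practice effect, so it supplements the actor review and does not replace it.

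**Conclusion.** The omission is confirmed, but no change to the plan is needed. Nothing in Aim 2 or Section 7 rests on the actor ratings, so the effect on planned conclusions is nil. For an unplanned report of fidelity change, the size of any bias is unknown. The illustrative 25%, 50% and 75% are shares of an unspecified drift under an assumed numeric score and a single linear sequence in visit order. They are not estimates for this study.

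The conclusion rests on the measure staying outside the hypotheses and planned analyses. Rating order is a fair trade-off between protection from drift and a rating workload deferred to the end, and the team can make that choice in its working procedures. Task familiarity and changes in actor performance would remain after any masking, so in this single-group design a reported change would be uncontrolled in either case.
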